10.4.3. Phase 2 Safety Analysis

All safety analyses will be conducted in the safety population.

AEs will be coded according to the Medical Dictionary for Regulatory Activities (MedDRA), version 21.0, or higher. The severity of AEs will be graded according to NCI CTCAE, version 5.0.

Treatment-emergent adverse events (TEAEs) are defined as any AE occurring or worsening on or after the first study drug dose and within 30 days after the last dose date. TEAEs, TEAEs leading to study drug discontinuation, TEAEs leading to dose reduction/interruption, TEAEs related to study drug, SAEs, and TEAEs with an outcome of death will be summarized by system organ class, and preferred term for each treatment group. A summary of TEAEs of NCI CTCAE Grade 3 or higher, as well as the most frequent TEAEs (preferred terms), and TEAEs by relationship to study treatment, will be provided. AE incidence rates will also be summarized adjusting for duration of study treatment.

Values and changes from baseline in clinical laboratory results will be summarized by visit. Clinical laboratory values will be graded according to NCI CTCAE 5.0, for applicable tests. Shifts in toxicity grades from baseline grade will be summarized.

Vital signs, ECG, and concomitant medication data will be summarized. Graphical displays will be provided where useful to assist in the interpretation of results.

10.5. Phase 2 Dose Escalation Cohort Review Committee (CRC)

During the Phase 2 dose escalation study, a CRC, comprising relevant site investigators, the Medical Monitor, and Sponsor representatives, will oversee safety, cohort evaluation and dose-escalation for the study. A formal charter which will establish the rules, meeting frequency and scope of responsibilities of the CRC will be established for the conduct of the CRC.

Investigational Product: IMU-131
Protocol Identifier: IMU.ACS.001
Protocol Version: Protocol Global Amendment #5, 27 September 2023

Toxicity data for each cohort will be reviewed prior to dose escalation approval by CRC. Each CRC meeting will be held after each dose cohort has completed Day 35 and prior to initiation of the next dose cohort. The CRC will review the complete, pre-defined safety dataset from each dose cohort and will determine, with advice from the Medical Monitor, the appropriate dose limiting toxicity (DLT) rule (see [Section 10.5.1](#) Definition of Dose-Limiting Toxicity and [Section 10.5.2](#) Dose Escalation Decision Rules, for details) and whether the study will proceed to the next dose cohort. A dose cohort must have completed Day 35 of the study, including 3 doses of IMU-131 and 1 cycle of chemotherapy prior to the CRC meeting and opening of the next higher dose cohort for enrollment. All DLTs will be reviewed by CRC irrespective of whether patients receive 1, 2, or 3 doses of IMU-131 during the DLT assessment period.

The CRC will review all available safety/tolerability and immunogenicity data and make recommendations regarding dose escalation and the continuation of the study following the procedures outlined in the CRC charter.

All decisions will be documented in the form of minutes.

10.5.1. Phase 2 Dose Escalation Definition of Dose-Limiting Toxicity (DLT)

A dose limiting toxicity (DLT) is defined as an IMU-131-related Grade 3 toxicity that cannot be resolved to a Grade 1 with appropriate therapy within 2 weeks, or a Grade 4 or greater toxicity graded by CTCAE v5.0, related to the IMU-131 vaccine.

In addition, after enrollment in Phase 2 dose escalation begins, the CRC will meet by teleconference as soon as feasible after any of the following occur to determine if the criteria for dose limiting toxicity (DLT) has been met:

- One or more patients experience a serious adverse reaction assessed as related to the vaccine by the investigator.
- One or more patients experience anaphylaxis.

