6.5.2. Contraindications to repeated vaccination

If any of the following adverse events arise during the study they constitute contraindications to further administration of IMU-131, and patients should discontinue IMU-131 treatment permanently and be withdrawn from the study immediately, with appropriate safety follow-up by the investigator until resolution of the event, as with any adverse event (see [Section 9: Adverse Event Reporting](#)):

- Anaphylactic reaction following the administration of vaccine(s).
- Any clinically relevant immunosuppressive or immuno-deficient condition.

The following events constitute contraindications to administration of IMU-131. If an adverse event, the event must be reported and the patient followed as with any adverse event. Withdrawal of patients experiencing the following events is at the discretion of the investigator as indicated below:

- Acute illness at the time of vaccination. Acute illness is defined as the presence of a moderate or severe illness with or without fever. All vaccines can be administered to persons with a minor illness such as diarrhea, mild upper respiratory infection with or without low-grade febrile illness, i.e., temperature $<38^{\circ}\text{C}$. Withdrawal is at the discretion of the investigator if acute illness will not resolve in sufficient time to allow for vaccination schedule to continue.
- Temperature $\geq 38^{\circ}\text{C}$ at the time of vaccination. Withdrawal is at the discretion of the investigator if raised temperature will not resolve in sufficient time to allow for vaccination schedule to continue.

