10.5.2. Phase 2 Dose Escalation

Between 3 - 6 patients will be enrolled in each Phase 2 dose escalation cohort for safety evaluation by CRC prior to next dose being opened to enrollment. The CRC will review data from one complete cycle of chemotherapy and 3 doses of IMU-131, for at least 3 patients in a dose cohort to authorize dose escalation. The DLT window is 35 days.

Dose escalation in Phase 2 will start at 100 μ g IMU-131, within a standard 3 + 3 scheme for determination of safety prior to opening enrollment to the 200 μ g IMU-131 dose cohort. A dose cohort must be reviewed by CRC for DLTs according to dose escalation decision rules before opening the next dosed cohort.

Either the 100 μ g or 200 μ g dose escalation cohort may be expanded up to 10 patients after CRC clearance of the 35-day DLT period.

Phase 2 Dose Escalation Decision Rules:

- If 0 out of 3 patients with treatment DLT at a given IMU-131 dose level, enter 3 patients at the next dose level;
- If ≥ 2 of 3 patients with treatment related DLT at a given dose level, dose escalation will be stopped. This dose level will be declared the maximally administered dose (highest dose administered). Three (3) additional patients will be entered at the next lower dose level if only 3 patients were treated previously at that dose;
- If 1 out of 3 patients with treatment related DLT at a given dose level, enter at least 3 more patients at this dose level. If 0 of these 3 patients experience treatment related DLT, proceed to the next dose level. If 1 or more of this group suffer treatment related DLT, then dose escalation is stopped, and this dose is declared the maximally administered dose. Three (3) additional patients may be entered at a dose between the current dose and the next lowest dose level, the exact dose of which will be determined by the CRC.

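### Phase 2 Extension: a vaccine-related Grade 3 anaphylaxis that resolves within 2 weeks permanently stops the patient's vaccination but is not a DLT, so after dose 3 the 3+3 count can still read 0 of 3 and point to 200 µg

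*Protocol*

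**What the plan says.** **DLT definition.** Protocol 10.5.1, and the two statements of the definition in the synopsis (Safety Monitoring, Phase 2 Extension), have two limbs. One is any vaccine-related toxicity of Grade 4 or greater. The other is "an IMU-131-related Grade 3 toxicity that cannot be resolved to a Grade 1 with appropriate therapy within 2 weeks".

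**Anaphylaxis in the same section.** "One or more patients experience anaphylaxis" is one of two triggers for a prompt CRC teleconference. The stated task of that meeting is to decide whether the DLT criteria are satisfied.

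**Permanent stop.** Protocol 6.5.2 lists an anaphylactic reaction to the vaccine, with no limit on grade or duration, among the events after which "patients should discontinue IMU-131 treatment permanently and be withdrawn from the study immediately".

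**Escalation rule.** Protocol 10.5.2: "If 0 out of 3 patients with treatment DLT at a given IMU-131 dose level, enter 3 patients at the next dose level". One DLT in 3 requires at least 3 more patients at the same dose. Two or more in 3 stop escalation.

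**Minimum data.** The CRC reviews one full chemotherapy cycle and "3 doses of IMU-131, for at least 3 patients in a dose cohort to authorize dose escalation". Also in 10.5.2: "Between 3 - 6 patients will be enrolled in each Phase 2 dose escalation cohort for safety evaluation by CRC" and "The DLT window is 35 days".

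**Committee.** Under 10.5 the CRC sees all available safety data, decides whether to open the next cohort, and works to a charter that was not available for this review. DLTs are reviewed whether the patient had 1, 2 or 3 doses.

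**The concern.** The DLT definition and the stopping rule treat the same event differently. For the individual patient, a resolved Grade 3 anaphylaxis is serious enough to end vaccination for good. For the cohort, it leaves the DLT count unchanged. Prompt treatment, which the protocol requires sites to be equipped to give, is also what removes the event from the count.

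Safety and tolerability at 100 and 200 µg is the Extension's primary objective, and treatment-emergent adverse events leading to discontinuation are part of its primary endpoint. These doses are 2 and 4 times the 50 µg given in Phase 2. Protocol 1.4 names anaphylaxis as a possible risk and reports none so far. The 3+3 count is the escalation criterion that the protocol fixes in advance, before the committee exercises judgement.

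**Working it through.** The Extension has no formal sample-size calculation and states no operating characteristic, so there is no planned figure to reproduce. The check applies 10.5.1 and 10.5.2 to specific cases and then to assumed rates.

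**Which anaphylaxis counts (10.5.1)**

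| Vaccine-related anaphylaxis | DLT? | Permanent stop (6.5.2)? |
|---|---|---|
| Grade 4 or higher | Yes | Yes |
| Grade 3, not back to Grade 1 in 2 weeks | Yes | Yes |
| Grade 3, back to Grade 1 in 2 weeks | **No** | Yes |

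**What the count does at 100 µg (3 patients, no other DLTs)**

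| Resolved Grade 3 anaphylaxis | As written | If it counted |
|---|---|---|
| 1 of 3, after dose 3 | 0 of 3: next dose | 1 of 3: at least 3 more at this dose |
| 2 or 3 of 3, after dose 3 | 0 of 3: next dose | 2 or more of 3: stop |
| 1 of 3, after dose 1 or 2, not replaced | 2 patients with 3 doses: cannot escalate | 1 of 3: at least 3 more at this dose |

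A patient who reacts after dose 3 on Day 35 has had 3 doses and a full 21-day chemotherapy cycle, so meets the minimum for CRC review. That patient then loses every booster from Day 77 on.

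**Illustrative size.** The documents give no rate. Assume a per-patient chance r = 5%, 10%, 20% of a related, resolved Grade 3 anaphylaxis, and no other DLTs.

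Let p0 = (1−r)³ and p1 = 3r(1−r)².
- p0 = 0.8574, 0.7290, 0.5120
- p1 = 0.1354, 0.2430, 0.3840

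*All risk at dose 3, no replacement:*
- Count reads 0 of 3 despite at least 1 reaction: 1 − p0 = 0.143, 0.271, 0.488
- Despite at least 2: 1 − p0 − p1 = 0.007, 0.028, 0.104
- Rule points to the next dose, as written: 1.00 at every r, which follows from assuming no other DLTs
- If such reactions counted: p0 + p1·p0 = 0.973, 0.906, 0.709
- Difference: about 3, 9 and 29 points

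*Risk split equally over three doses, counting dose-3 reactions only:* replace r by r/3 = 1.67%, 3.33%, 6.67%.
- If such reactions counted: (1−r/3)³ + 3(r/3)(1−r/3)⁵ = 0.997, 0.988, 0.955
- Difference: about 0.3, 1.2 and 4.5 points

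*All risk at dose 1 or 2:*
- As written, stopped patients replaced one for one up to 6: P(at least 3 of 6 have 3 doses) = 0.9999, 0.9987, 0.9830
- As written, not replaced: p0 = 0.857, 0.729, 0.512
- If such reactions counted: 0.973, 0.906, 0.709

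On this last route the present text is looser than the fix if stopped patients are replaced, and stricter if they are not. All figures describe the numeric rule before any CRC decision.

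**The case against.** The strongest reply is that the plan handles anaphylaxis by mandatory expert review instead of an automatic count. A single case calls a CRC meeting. A reaction that is also a related serious event would fire the second trigger. The CRC sees all safety data and decides whether the next cohort opens. The charter may add rules. Known diphtheria toxoid hypersensitivity is excluded, each vaccination is followed by at least 30 minutes of observation, and Phase 1b used the same 2-week condition.

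This limits the consequence but does not change the count. The meeting tests the event against the same DLT criteria, and the provision on 1, 2 or 3 doses covers only events already classed as DLTs.

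The reply does rule out several stronger readings that a reader might infer:
- *That the count ignores anaphylaxis.* It does not. Grade 4 or higher, and Grade 3 that fails to resolve in 2 weeks, both count.
- *That escalation would follow automatically, or that only CRC discretion holds the dose.* The CRC may decline to escalate, and what else binds it cannot be stated without the charter.
- *That reactions after dose 1 or 2 slip through in the same way.* They do so only if stopped patients are replaced. The 3-to-6 range leaves room for that, but no replacement rule is written. Without replacement, fewer than 3 of 3 patients have 3 doses and escalation cannot be authorized.
- *That the effect is 29 points.* That needs a 20% rate with all of it at dose 3.

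Nothing in the documents shows that anaphylaxis to this vaccine depends on dose, so one idiosyncratic case could slow escalation. That is a real cost of the fix.

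**Conclusion.** The point holds in a narrow form. The pre-specified DLT count for the Extension omits related Grade 3 anaphylaxis that resolves within 2 weeks, although 6.5.2 treats it as a permanent stop. The clear route is a reaction after dose 3, where one or more such reactions among 3 patients still read 0 of 3. This is a defect in the written count. It is not evidence that the CRC would escalate.

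The reading of the text needs no assumption. The size does: it rests on assumed rates of 5% to 20%, no other DLTs, and how the risk is spread over the doses. Depending on that spread, the change in the chance that the rule clears a dose runs from about 0.3 points (5%, split equally, dose-3 reactions only) to about 29 points (20%, all at dose 3). The change is worth making because it is cheap and bears on the Extension's primary objective.

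**What to change.** Add one clause to the DLT definition in Protocol 10.5.1 and to both statements of it in the synopsis, and mirror it in the CRC charter: *or any IMU-131-related anaphylaxis of Grade 3 or higher after any of the first 3 doses, even if it resolves to Grade 1 within 2 weeks.*

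Leave 10.5.2 unchanged. Tying the clause to the dose and not to the calendar also covers a third dose given on Day 36 to 38 under the ±3-day visit window, which would otherwise sit awkwardly with a 35-day DLT window. Because 10.5 already has DLTs reviewed after 1, 2 or 3 doses, a patient stopped early enters the count as well.

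No new data are needed. The cost is that a single idiosyncratic case in the first 3 patients requires 3 more patients at that dose, within the existing 3-to-6 range, and a second case stops escalation.

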10.5.2. Phase 2 Dose Escalation

Between 3 - 6 patients will be enrolled in each Phase 2 dose escalation cohort for safety evaluation by CRC prior to next dose being opened to enrollment. The CRC will review data from one complete cycle of chemotherapy and 3 doses of IMU-131, for at least 3 patients in a dose cohort to authorize dose escalation. The DLT window is 35 days.

Dose escalation in Phase 2 will start at 100 μ g IMU-131, within a standard 3 + 3 scheme for determination of safety prior to opening enrollment to the 200 μ g IMU-131 dose cohort. A dose cohort must be reviewed by CRC for DLTs according to dose escalation decision rules before opening the next dosed cohort.

Either the 100 μ g or 200 μ g dose escalation cohort may be expanded up to 10 patients after CRC clearance of the 35-day DLT period.

Phase 2 Dose Escalation Decision Rules:

- If 0 out of 3 patients with treatment DLT at a given IMU-131 dose level, enter 3 patients at the next dose level;
- If ≥ 2 of 3 patients with treatment related DLT at a given dose level, dose escalation will be stopped. This dose level will be declared the maximally administered dose (highest dose administered). Three (3) additional patients will be entered at the next lower dose level if only 3 patients were treated previously at that dose;
- If 1 out of 3 patients with treatment related DLT at a given dose level, enter at least 3 more patients at this dose level. If 0 of these 3 patients experience treatment related DLT, proceed to the next dose level. If 1 or more of this group suffer treatment related DLT, then dose escalation is stopped, and this dose is declared the maximally administered dose. Three (3) additional patients may be entered at a dose between the current dose and the next lowest dose level, the exact dose of which will be determined by the CRC.

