	
Treatment Visit for Phase 1b will be maintained on booster doses of IMU-131 starting from Day 98.
 
Duration of treatment in Phase 1b
 
Each patient will be administered 3 injections of IMU-131 (P467-CRM197-Montanide emulsion), at a single dose level on Days 0, 14, and 35, accompanied by chemotherapy cycles every 21 days starting from Day 14. Chemotherapy will be ceased by the investigator when clinically indicated for the care of the patient. Patients will be discontinued from the study and cease IMU-131 vaccinations when there is documented evidence of disease progression according to the Response Evaluation Criteria In Solid Tumors (RECIST 1.1) or if unacceptable toxicity occurs (see Section 6.5 Patient Withdrawal for complete discontinuation criteria).
 
Part 2 consists of Phase 2: Evaluation of exploratory clinical activity of IMU-131
 
Phase 2 will enroll approximately 36 patients and be conducted in the same centers with the addition of new centers, as required, to fulfill recruitment. Phase 2 will have similar inclusion/exclusion criteria and be conducted according to a similar schedule of events and study procedures. During conduct of the Phase 1b study and prior to the start of Phase 2, an amendment to the current protocol will be submitted for ethical and regulatory review. The Phase 2 evaluation of clinical activity of IMU-131 will be initiated after approval of Phase 2 and upon completion of Phase 1b (all cohorts completed through Day 56 and selection of a RP2D of IMU-131).
 
Phase 2 is an open-label randomized comparison of IMU-131 plus standard of care chemotherapy versus standard of care chemotherapy alone. Patients will be randomly assigned to either 'IMU-131 plus chemotherapy' or 'chemotherapy alone' groups. Treatment for both groups will begin at the Baseline/Day 0 visit.
 
The IMU-131 plus chemotherapy group will receive vaccination of IMU-131 at Baseline/Day 0, Day 14, Day 35, Day 77, Day 140 and then every 63 days until disease progression.
 
Both the IMU-131 plus chemotherapy group and the chemotherapy alone group will receive chemotherapy starting at the Baseline/Day 0 Visit and then every 21 days for a maximum of 6 cycles as clinically indicated or until disease progression, whichever occurs sooner.
 
Phase 2 Extension
 
Dose escalation during Phase 2 is an open-label, multicenter, single arm dose escalation study with the same inclusion/exclusion criteria as Phase 2 and the same schedule of assessments (SoA) as Phase 2 IMU-131+chemotherapy arm. Patients will no longer be followed for post treatment follow up. The safety of each dose will be assessed by CRC after at least 3 patients have 3 doses of IMU-131 and one cycle of chemotherapy and have completed the 35 day DLT window. Two dose cohorts, consisting of 100μg and 200μg dose levels of IMU-131, will

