- Record adverse events;
- Initiate chemotherapy cycle 1.

6.4.3. Phase 2 and Phase 2 Extension Week2/Day 14 (only for patients in IMU-131 plus chemotherapy cohorts)

The visit window for Day 14 is +/- 3 days of the scheduled visit. Day 14 procedures should be performed in the following order:

- Weight, and vital signs (blood pressure, temperature and heart rate);
- Urine pregnancy test (female);
- Administer IMU-131 vaccination;
- Record body temperature 30 (+/-10) minutes after vaccination;

Investigational Product: IMU-131
Protocol Identifier: IMU.ACS.001
Protocol Version: Protocol Global Amendment #5, 27 September 2023

- Record concomitant treatments;
- Record adverse events.

6.4.4. Phase 2 and Phase 2 Extension Week 3/Day 21

The visit window for Day 21 is +/- 3 days of the scheduled visit. Day 21 procedures should be performed in the following order:

- Blood sample for hematology and serum chemistry;
- Blood sample for humoral immunology;
- Weight, and vital signs (blood pressure, temperature and heart rate);
- Urine pregnancy test (female);
- Physical examination;
- Record concomitant treatments;
- Record adverse events;
- Initiate chemotherapy cycle 2.

6.4.5. Phase 2 and Phase 2 Extension Week 5/Day 35 (only for patients in IMU-131 plus chemotherapy cohorts)

The visit window for Day 35 is +/- 3 days of the scheduled visit. Day 35 procedures should be performed in the following order:

- Weight, and vital signs (blood pressure, temperature and heart rate);
- Urine pregnancy test (female);
- Administer IMU-131 vaccination;
- Record body temperature 30 (+/-10) minutes after vaccination;
- Record concomitant treatments;
- Record adverse events.

6.4.6. Phase 2 and Phase 2 Extension Week 6/Day 42

The visit window for Day 42 is +/- 3 days of the scheduled visit. Day 42 procedures should be performed in the following order:

- Blood sample for hematology and serum chemistry;
- Blood sample for humoral immunology;
- Weight, and vital signs (blood pressure, temperature and heart rate);
- Urine pregnancy test (female);
- Physical examination;
- Radiographic assessment;
- Record concomitant treatments;

Investigational Product: IMU-131
Protocol Identifier: IMU.ACS.001
Protocol Version: Protocol Global Amendment #5, 27 September 2023

- Record adverse events;
- Initiate chemotherapy cycle 3.

6.4.7. Phase 2 and Phase 2 Extension Week 9/Day 63

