The visit window for Day 63 is +/- 7 days of the scheduled visit. Day 63 procedures should be performed in the following order:

- Blood sample for hematology and serum chemistry;
- Blood sample for humoral immunology;
- Weight, and vital signs (blood pressure, temperature and heart rate);
- Urine pregnancy test (female);
- Physical examination;
- Record concomitant treatments;
- Record adverse events;
- Initiate chemotherapy cycle 4.

6.4.8. Phase 2 and Phase 2 Extension Week 11/Day 77 (only for patients in IMU-131 plus chemotherapy cohorts)

The visit window for Day 77 is +/- 7 days of the scheduled visit. Day 77 procedures should be performed in the following order:

- Weight, and vital signs (blood pressure, temperature and heart rate);
- Urine pregnancy test (female);
- Administer IMU-131 vaccination;
- Record body temperature 30 (+/-10) minutes after vaccination;
- Record concomitant treatments;
- Record adverse events.

6.4.9. Phase 2 and Phase 2 Extension Week 12/Day 84 (Repeat every 12 weeks/84 days)

The visit window for Day 84 is +/- 7 days of the scheduled visit. Day 84 procedures should be performed in the following order:

- Weight, and vital signs (blood pressure, temperature and heart rate);
- Blood sample for hematology and serum chemistry;
- Blood sample for humoral and cellular immunology;
- Blood sample for exploratory endpoints;
- Urine pregnancy test (female);
- Physical examination;
- ECOG performance score;

Investigational Product: IMU-131
Protocol Identifier: IMU.ACS.001
Protocol Version: Protocol Global Amendment #5, 27 September 2023

- Cardiac assessment by echocardiography or MUGA scan and 12-lead ECG;
- Radiographic assessment;
- Optional tumor biopsy sample (at Day 84);
- Record concomitant treatments;
- Record adverse events;
- Initiate chemotherapy cycle 5.

6.4.10. Phase 2 and Phase 2 Extension Week 15/Day 105

The visit window for Day 105 is +/- 7 days of the scheduled visit. Day 105 procedures should be performed in the following order:

- Blood sample for hematology and serum chemistry;
- Weight, and vital signs (blood pressure, temperature and heart rate);
- Urine pregnancy test (female);
- Physical examination;
- Record concomitant treatments;
- Record adverse events;
- Initiate chemotherapy cycle 6.

6.4.11. Phase 2 and Phase 2 Extension Week 18/Day 126 (Repeat every 12 weeks/84 days)

The visit window for Day 126 is +/- 7 days of the scheduled visit. Day 126 procedures should be performed in the following order:

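### In the Phase 2 Extension, the CRC may clear escalation or expansion with only 0 to 3 days of follow-up after dose 3 in the last-dosed patient

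*Protocol*

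**What the plan says.** Extension patients receive IMU-131 on Days 0, 14 and 35. Protocol 6.4.5 adds: "The visit window for Day 35 is +/- 3 days of the scheduled visit". That visit covers weight, vital signs, a pregnancy test, the injection, a temperature reading about half an hour later, and recording of treatments and adverse events. It has no safety labs. Protocol 8.6 places safety labs at Day 21 and next at Day 42.

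On the gate, 10.5.2 says "The DLT window is 35 days", and 10.5 says: "A dose cohort must have completed Day 35 of the study, including 3 doses of IMU-131 and 1 cycle of chemotherapy" before the CRC meets and the next dose opens. The synopsis says the same: at least three patients have had three doses and one chemotherapy cycle "and have completed the 35 day DLT window". Clearance of the 35-day period also permits expansion of either cohort to 10 patients.

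Under 10.5.1 a related Grade 3 toxicity is a DLT only if it "cannot be resolved to a Grade 1 with appropriate therapy within 2 weeks". Sections 10.6 and 10.6.2 use Day 42 as a condition for analysis and reporting, not for CRC clearance.

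The protocol also contains safeguards. Section 10.5 states: "The CRC will review all available safety/tolerability and immunogenicity data". It also has the CRC examine a full safety dataset fixed in advance, and it counts DLTs after one, two or three doses. Under 10.5.1 a related serious reaction or anaphylaxis triggers an ad hoc meeting.

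**The concern.** Dose 3 is a condition for clearance, but nothing in 10.5 or 10.5.2 requires time after it. The last patient in a cohort can be counted as DLT-free on the day of the third injection, and an open related Grade 3 event has no stated status.

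In a 3+3 scheme one patient decides the outcome. With 0 of 3 the next dose opens; with 1 of 3 at least three more patients are treated at the same dose. The decision opens 200 µg, when earlier phases went no higher than 50 µg, or enlarges a cohort to 10.

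Protocol 1.3 shows that the kinds of event at issue do occur. One patient at 50 µg had Grade 1 redness and itch starting 3 days after the third injection, which is later than the shortest follow-up the gate allows. Another had Grade 3 hyponatremia judged related, while no serious adverse reaction was reported. Neither was a DLT, and the onset day of the hyponatremia is not given. They show that delayed reactions and non-serious related Grade 3 laboratory events happen, not how often they would fall beyond the gate.

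**Working it through.** No power formula applies, because 10.7.3 gives no formal sample size. The check is day arithmetic on the stated dosing days and visit windows.

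**The plan's own figure.** Day 0 to Day 35 is 35 days, the nominal day of dose 3. In Phase 1b, Day 35 was also the end of chemotherapy cycle 1 (start Day 14, 14 + 21 = 35). In the Extension chemotherapy starts on Day 0, so cycle 1 ends on Day 21.

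**Nominal follow-up to Day 35.**
- Dose 1: 35 − 0 = 35 days
- Dose 2: 35 − 14 = 21 days
- Dose 3: 35 − 35 = 0 days

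**Follow-up after dose 3 at the earliest clearance.** Because three doses are required, earliest clearance = max(Day 35, day of dose 3).
- Dose 3 on Day 32: 35 − 32 = 3 days
- Dose 3 on Day 35: 35 − 35 = 0 days
- Dose 3 on Day 38: 38 − 38 = 0 days

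**Open Grade 3 events.** The latest onset that completes 2 weeks by Day 35 is 35 − 14 = Day 21. Onset on Days 22 to 35 (14 of 35 days) may be undetermined at a Day 35 meeting. This is a count of calendar days, not a probability.

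**Safety labs.** The nominal gap is 42 − 21 = 21 days. Section 6.4.6 says "The visit window for Day 42 is +/- 3 days of the scheduled visit", so the Day 42 visit (Days 39 to 45) can fall from 39 − 38 = 1 to 45 − 32 = 13 days after dose 3. Table 3 footnote M allows labs up to 72 hours before a visit, so they could precede dose 3: 39 − 3 − 38 = −2 days.

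**Other patients in the cohort.** Assume even accrual of 20 patients over 15 months: 15 × 30.44 = 457 days, and 457 / 20 = 22.8 days per patient. When the last of three reaches the gate, the other two have about 23 and 46 days after dose 3. If three patients start almost together, all are near the minimum.

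**A 7-day rule against the existing schedule.** The earliest qualifying day is 32 + 7 = 39, 35 + 7 = 42 or 38 + 7 = 45, always inside Days 39 to 45. Labs drawn 72 hours before such a visit are at least 7 − 3 = 4 days after dose 3. A 14-day rule would need Days 46 to 52, where no visit exists: the Day 42 window ends on Day 45 and, since "The visit window for Day 63 is +/- 7 days of the scheduled visit", the next opens on 63 − 7 = Day 56.

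**Delay relative to the earliest clearance.**
- Dose 3 on Day 32: visit Day 39 to 45 against Day 35, 4 to 10 days
- Dose 3 on Day 35: visit Day 42 to 45 against Day 35, 7 to 10 days
- Dose 3 on Day 38: visit Day 45 against Day 38, 7 days
- Related Grade 3 event starting at the end of the period: add 14, giving 18 to 24 days, or about 3 weeks

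**Booster wording (separate).** The synopsis dose-and-schedule text and Protocol 5.2.3 put 63-day intervals straight after Day 35, so the next dose is 35 + 63 = Day 98. The synopsis study-drug text and sections 6.4.8 and 6.4.12 give Days 77 and 140, matching Protocol 1.3: 35 + 42 = 77 and 77 + 63 = 140. The first booster differs by 98 − 77 = 21 days.

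**The case against.** The strongest objection is that the working rules sit elsewhere. Section 10.5 refers procedures to a CRC charter, and 10.6.1 says the charter governs this part of the study. A data-maturity rule and the handling of open Grade 3 events could be there. The CRC reviews a full predefined dataset, may use everything available and has discretion to hold. Section 1.4 adds regular site teleconferences, and 9.2 runs adverse event reporting to 28 days after the last dose. The synopsis reports no IMU-131-related safety signals or DLTs so far, and Phase 1b used the same Day 35 gate.

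Much of this stands. It limits the gap to recently dosed patients and mainly to events that are not serious. It does not close it: none of these provisions, as written, sets a minimum time after dose 3, and the reassuring experience stops at 50 µg.

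A reader might infer more than the documents support:
- **That cohorts will routinely be cleared with no follow-up after dose 3.** Zero days is the floor for the last patient at the earliest meeting.
- **That the window can close 3 days before a late dose 3.** Section 10.5 requires three doses and treats all three as inside the assessment period, so clearance waits for a late dose.
- **That the chance of passing a toxic dose can be quantified.** That needs a true DLT rate and the share of DLTs appearing after the gate; the documents give neither.
- **That the Extension loosened the Phase 1b gate.** Phase 1b had a Day 37 injection-site check that the Extension lacks, but 10.1.2 did not make it a condition for clearance.
- **That the primary endpoint is truncated.** TEAE incidence is not limited by the 35-day window.

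**Conclusion.** The point holds as a gap in the escalation and expansion gate, and it should be fixed. The protocol permits clearance with 0 to 3 days of follow-up after dose 3 in the last-dosed patient, no safety labs since the Day 21 visit, and a related Grade 3 event with onset after Day 21 possibly unresolved as to DLT status. What is exposed is mainly non-serious related Grade 3 events or laboratory toxicity in recently dosed patients.

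The day counts follow from the protocol. That a meeting would be held at the earliest moment is an assumption, as is even accrual for the other patients. The conclusion concerns the protocol text: if the charter already imposes a wait, the remedy is to bring that rule into the protocol. Confidence is medium for that reason. The booster mismatch has no bearing on the DLT window; the visit schedule already settles it and only the wording needs correcting.

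**What to change.** In 10.5, 10.5.2 and the synopsis, require the following before CRC clearance:

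- Each patient counted as DLT-free has received dose 3 and completed the Day 42 visit at least 7 days after the actual third dose, with safety labs drawn after that dose.
- A patient who already has a DLT is counted as such and needs no further dose or follow-up for the gate. The rule that DLTs count after one, two or three doses stays.
- A patient who stops before dose 3 without a DLT is either replaced or followed through the Day 42 visit, as the CRC decides. Without this, one early stop could block clearance.
- Clearance is held while any IMU-131-related Grade 3 event with onset in this period is within its 2-week resolution period.

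Seven days is a judgement: it is what the existing visits can carry, and the documents give no onset data that fix a length.

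The cost is protocol wording and about 4 to 10 days per review, or about 3 weeks when a related Grade 3 event starts late. Two reviews are planned, with up to four if both cohorts are enlarged to 6. At about 7 days each, that is 2 × 7 = 14 days (14 / 457 = 3% of recruitment) to 4 × 7 = 28 days (28 / 457 = 6%). If both planned reviews were held for a late Grade 3 event, it would be 2 × 21 = 42 days (42 / 457 = 9%). When dose 3 is late, the Day 42 visit may have to be as late as Day 45; if it was held too early, that patient needs a further check and possibly repeat labs.

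Separately, and at no cost, correct the synopsis dose-and-schedule text and Protocol 5.2.3 so that Extension vaccinations fall on Days 0, 14, 35, 77 and 140, with 63-day intervals from there, as in the synopsis study-drug text and sections 6.4.8 and 6.4.12.
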